6.4.3 Exploratory Efficacy Endpoint

The proportion of patients with disease activity at Week 24 will be reported with the corresponding 80% Wilson score confidence intervals by study arm.

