1.3 STUDY RATIONALE AND BENEFIT-RISK ASSESSMENT

As a result of the chronic, progressive nature of nAMD, frequent injections of currently available therapies over extended periods (e.g., monthly or bimonthly injections) are recommended. However, in routine clinical practice, such frequent office visits may not be practical or possible for all patients. Real-world data suggest many patients are under-treated with current therapies, leading to suboptimal outcomes (Cohen et al. 2013;

[Finger et al. 2013](#); [Holz et al. 2015](#)). In addition, a significant burden is placed on patients and their caregivers, as well as treating physicians and the healthcare system. A less frequent treatment administration schedule (e.g., every 3 or 4 months) that would provide visual acuity outcomes comparable to clinical trial results with frequent anti-VEGF monotherapy would therefore represent an important advance on currently available therapies, and would address the high unmet medical need for a more feasible treatment approach in nAMD patients.

RO6867461 binds to Ang-2, as well as to all isoforms of VEGF-A. Nonclinical data suggest the potential of adjunctive Ang-2 inhibition for both additional efficacy and prolonged duration of anti-leakage action ([Cheung et al. 2014](#); [von Leithner et al. 2014](#); [Heier 2016](#); [Regula et al. 2016](#)). This study will assess whether RO6867461 has the potential for administration at 12-week or 16-week intervals in further, larger scale studies of treatment-naive patients with nAMD. The study features four initial injections of the 6-mg dose followed by monthly assessment visits and fixed injections either every 12 weeks (Q12W) or every 16 weeks (Q16W). The extended initiation phase will allow patients to continue with frequent dosing during the “gain” phase of their treatment, aiming to maximize visual outcomes. The less frequent dosing thereafter is expected to, on average, at least maintain these initial gains. Only the 6-mg dose of RO6867461 will be utilized in this study to ensure sufficient VEGF-A and Ang-2 inhibition to permit less frequent dosing ([Hutton-Smith et al. 2016](#)). Patients will undergo monthly assessments throughout the study, with those patients intended for Q16W dosing undergoing a disease activity assessment at Week 24. Patients with anatomic or functional signs of disease activity at this timepoint will receive Q12W rather than Q16W dosing, in order to minimize the risk of under-treatment.

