2. OBJECTIVES AND ENDPOINTS

This study will evaluate the efficacy, safety, and pharmacokinetics of RO6867461 administered at 12- and 16-week intervals in patients with nAMD. Specific objectives and corresponding endpoints for the study are outlined below.

Table 1 Objectives and Corresponding Endpoints

Primary Efficacy Objective	Corresponding Endpoint

 To evaluate the efficacy of RO6867461 on visual acuity when administered at 12- and 16-week intervals 	
 Mean change from baseline BCVA at Week 40 using the ETDRS-like charts
Secondary Efficacy Objectives	Corresponding Endpoints

 To evaluate the efficacy of RO6867461 on additional visual acuity outcomes 	
 Mean change from baseline BCVA over time using the ETDRS-like charts Proportion of patients gaining ≥ 15, ≥ 10, ≥ 5, or ≥ 0 letters from baseline BCVA over time Proportion of patients avoiding loss of ≥ 15, ≥ 10, ≥ 5, or ≥ 0 letters from baseline BCVA over time Proportion of patients with BCVA of 20/40 or better over time Proportion of patients with BCVA of 20/200 or worse over time

 To evaluate the efficacy of RO6867461 on anatomic outcome measures using SD-OCT 	
 Mean change from baseline in CFT over time Mean change from baseline in mean CST (1 mm diameter) over time Proportion of patients with intraretinal fluid, subretinal fluid, cysts, or pigment epithelial detachment over time

 To evaluate the efficacy of RO6867461 on anatomic outcome measures using FFA 	
 Mean change from baseline in total area of CNV at Week 40 and Week 52 Mean change from baseline in total area of CNV component at Week 40 and Week 52 Mean change from baseline in total area of leakage at Week 40 and Week 52
Exploratory Efficacy Objective	Corresponding Endpoints

 To investigate the incidence of disease activity at Week 24 	
 Proportion of patients with disease activity at Week 24
Safety Objective	Corresponding Endpoints

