4.3.2 Dosage, Administration, and Compliance

4.3.2.1 RO6867461, Ranibizumab, and Sham

Patients will be given a 50- μ L IVT injection of RO6867461 or ranibizumab into the study eye, or a sham administration, according to the randomization schedule as described below (also see Section 3.1.1 and [Figure 1](#)).

- Arm A (Q12W): 6 mg RO6867461 IVT every 4 weeks up to Week 12 (4 injections), followed by 6 mg RO6867461 IVT every 12 weeks up to Week 48 (injections at Weeks 24, 36, and 48; 3 injections)
- Arm B (Q16W): 6 mg RO6867461 IVT every 4 weeks up to Week 12 (4 injections), followed by 6 mg RO6867461 IVT every 16 weeks up to Week 48 (injections at Weeks 28 and 44; 2 injections)
- Arm C (comparator arm): 0.5 mg ranibizumab IVT every 4 weeks for 48 weeks (13 injections)

Only one eye will be chosen as the study eye.

A protocol-defined assessment of disease activity at Week 24 requires patients in Arm B with active disease (see criteria in Section 4.5.5.4) to switch to a 12-weekly dosing regimen of 6 mg RO6867461 for the remainder of the study, with injections commencing at Week 24 and repeated at Weeks 36 and 48.

Sham IVT administration will be delivered to patients to maintain subject masking throughout the study period. In Arm A, sham IVT administrations will occur at Weeks 16, 20, 28, 32, 40, and 44. In Arm B, sham IVT administrations will occur at Weeks 16, 20, 24, 32, 36, 40, and 48, or at Weeks 16, 20, 28, 32, 40, and 44, the latter if the dosing regimen was switched to the 12-weekly schedule.

The Pharmacist responsible for dispensing the study treatment, or designated personnel, will prepare the correct study treatment (RO6867461, ranibizumab, or sham) as assigned by the IxRS.

Detailed stepwise instructions for the preparation of RO6867461, ranibizumab, or sham for administration, and mandatory materials to be used will be provided by the Sponsor, and are detailed in the Pharmacy Manual. Pre- and post-treatment administration procedures as well as instructions for performing the IVT and sham administrations are provided in [Appendix 3](#).

A specified filter needle must be used for each dose preparation of RO6867461 or ranibizumab as per the instructions provided in the Pharmacy Manual. All materials to prepare and administer study treatments will be provided by the Sponsor and no other material than provided should be used.

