4.5.5.4 Week 24 Assessment of Disease Activity

All patients will be assessed for disease activity at Week 24. Patients randomized to Arm B who have active disease at Week 24 (see criteria below) will switch to the Q12W dosing regimen of 6 mg RO6867461 for the remainder of the study, with injections commencing at Week 24 and repeated at Weeks 36 and 48.

Determination of active disease will be made if any of the following criteria are met:

- Increase in *CST* of $> 50 \mu\text{m}$ on Spectralis OCT compared to average *CST* over last 2 visits (Weeks 16 and 20)

Or

- Increase in *CST* of $\geq 75 \mu\text{m}$ compared to lowest *CST* recorded at either Week 16 or Week 20

Or

- Decrease of at least 5 letters of BCVA compared with average BCVA over last 2 visits (Weeks 16 and 20), due to nAMD disease activity
- Or**
- Decrease of ≥ 10 letters of BCVA compared to highest BCVA recorded at either Week 16 or Week 20 due to nAMD disease activity
- Or**
- Presence of new macular hemorrhage due to nAMD activity

If, in the opinion of the investigator, there is significant nAMD disease activity at Week 24 that requires immediate treatment, but does not meet the above criteria, the Medical Monitor should be contacted. In such cases, following approval by the Sponsor, patients randomized to Arm B will receive 6 mg RO6867461 at Week 24 and stay on repeated 12-weekly treatments at Weeks 36 and 48.

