6.4.1 Primary Efficacy Endpoint

The primary efficacy endpoint is BCVA change from baseline at Week 40. The primary efficacy analysis will be performed using a Mixed Model for Repeated Measurement (MMRM) model. The model will include the categorical covariates of treatment group, visit, and visit by treatment group interaction and the continuous covariate of baseline BCVA. An unstructured covariance will be used to account for within-patient correlation, but another variance-covariance structure, such as AR(1), may be selected in case of convergence issues.

Means for RO6867461 and ranibizumab arms, difference of the means relative to ranibizumab, and the corresponding two-sided 80% confidence intervals will be computed. There will not be formal correction for multiple testing.

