6.4.2 Secondary Efficacy Endpoints

Mean change from baseline BCVA over time using the ETDRS-like charts will be analyzed using the MMRM model described in Section 6.4.1.

Categorical outcomes measured repeatedly will be analyzed using Generalized Estimating Equations with a binomial distribution, logit link function, and unstructured covariance. In case of convergence issues, AR(1) covariance structure will be used. The model will include the categorical covariates of treatment group, visit, and visit by treatment group interaction. Least squares means with the corresponding two-sided 80% confidence intervals and odds ratios will be computed.

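### Week 24 disease activity is reported by arm only, although Arms A and B have the same planned treatment until then; a pooled A+B row would be about 28-29% more precise

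*Combined protocol and SAP*

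**What the plan says.** The Week 24 endpoint is exploratory and has one planned analysis (Section 6.4.3): "The proportion of patients with disease activity at Week 24 will be reported with the corresponding 80% Wilson score confidence intervals by study arm". Section 4.5.5.4 applies the assessment to every arm: "All patients will be assessed for disease activity at Week 24". The result changes dosing only in Arm B, where patients with active disease move to the Q12W schedule starting at that visit.

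Sections 3.1.1 and 4.3.2.1 give both RO6867461 arms the same four injections, every 4 weeks up to Week 12. The sham schedules then read "In Arm A, sham IVT administrations will occur at Weeks 16, 20, 28, 32, 40, and 44" and, for Arm B patients who are not switched, "In Arm B, sham IVT administrations will occur at Weeks 16, 20, 24, 32, 36, 40, and 48". The schedule for switched Arm B patients also has sham at Weeks 16 and 20. The two arms first differ in planned treatment at the Week 24 administration, after the assessment.

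For visual acuity, Section 6.4.1 states: "Means for RO6867461 and ranibizumab arms, difference of the means relative to ranibizumab, and the corresponding two-sided 80% confidence intervals will be computed". Section 6.4.2 uses the same model for BCVA over time. For repeated categorical outcomes it says "Least squares means with the corresponding two-sided 80% confidence intervals and odds ratios will be computed" and does not name the reference group. No section specifies a pooled A+B estimate or a B-versus-A contrast.

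**The concern.** By Week 24, randomisation to A or B has not yet produced any planned difference in treatment. A table by arm alone splits the data on one quantity, the share of eyes active 12 weeks after the last of four monthly doses, into two halves. Each half has a wider interval than the data allow.

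Two arms under identical treatment will also often show different proportions by chance. A reader who sees the labels Q12W and Q16W above those proportions may take the gap for an effect of the regimen.

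This matters because the activity rate at 12 weeks is direct evidence on durability, and Section 1.3 gives the purpose as follows: "This study will assess whether RO6867461 has the potential for administration at 12-week or 16-week intervals in further, larger scale studies".

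**Working it through.** **Inputs.** About 75 patients randomised 2:2:1 (Section 3.1.1), with 30 per RO6867461 arm and 15 on ranibizumab, and an SD of BCVA change of 13.5 letters (Section 6.1). Intervals are two-sided 80%, so z = 1.2816. The documents give no Week 24 activity rate, so 20-50% is assumed. All randomised patients are taken as assessed at Week 24, because no dropout rate is given.

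**The plan's own figure.** RO6867461 versus ranibizumab: 1.2816 × 13.5 × √(1/30 + 1/15) = 5.47 letters. This reproduces the stated 5.5; t quantiles give 5.52 to 5.56.

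**Planned treatment before the assessment.** Both arms: active on Day 1 and at Weeks 4, 8 and 12; sham at Weeks 16 and 20. Time since the last active dose at Week 24 is 24 − 12 = 12 weeks in both.

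**Wilson interval.** Width = 2z√(p(1−p)/n + z²/4n²) / (1 + z²/n). At p = 0.35:

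- n = 30: 2 × 1.2816 × √(0.00758 + 0.00046) / 1.0547 = 0.218
- n = 60: 2 × 1.2816 × √(0.00379 + 0.00011) / 1.0274 = 0.156

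| Assumed rate | Width, one arm (n = 30) | Width, pooled (n = 60) | Reduction |
|---|---|---|---|
| 20% | 18.5 points (12.3-30.8%) | 13.2 points (14.2-27.4%) | 28.8% |
| 35% | 21.8 points | 15.6 points | 28.4% |
| 50% | 22.8 points (38.6-61.4%) | 16.3 points (41.8-58.2%) | 28.4% |

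The relative gain is close to 1 − 1/√2, so it would hardly change if some patients in both arms missed Week 24.

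**Chance differences between A and B.** With 30 per arm and the same true rate of 20-50%, the two observed proportions differ by 10 points or more in 42-52% of trials (exact binomial).

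**Pooled BCVA up to the pre-dose Week 24 assessment, using the same SD.**

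- RO6867461 mean: half-width 1.2816 × 13.5/√30 = 3.16 letters for one arm, and 1.2816 × 13.5/√60 = 2.23 pooled.
- Difference from ranibizumab: 1.2816 × 13.5 × √(1/60 + 1/15) = 4.99 letters instead of 5.47. The gain is small because Arm C has only 15 patients.

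**Arm B minus Arm A as assigned, after Week 24.** The half-width is 1.2816 × 13.5 × √(2/30) = 4.47 letters. Switched Arm B patients are dosed at Weeks 24, 36 and 48, as in Arm A, and so contribute no expected difference. If a share s of Arm B switches, the as-assigned difference is (1 − s) times the difference in patients kept on Q16W. Rescaled to those patients, with s treated as known, the half-width is 4.47/(1 − s):

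- s = 20% (assumed): 4.47/0.80 = 5.6 letters
- s = 50% (assumed): 4.47/0.50 = 8.9 letters

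Both exceed 5.47.

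**Weeks since the last injection (pre-dose) at Weeks 40/44/48/52.** Arm A and switched Arm B: 4/8/12/4. Non-switched Arm B: 12/16/4/8.

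**The case against.** The strongest reply is that this is a preference about display. The endpoint is exploratory, the trial is for estimation, reporting by arm is the usual default, and a reader with the two counts can add them and compute the pooled interval by hand. This stands in part: nothing in Section 6.4.3 is an error, and for the proportion the missing output is one row. It does not make the planned output as precise as the data allow.

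A second reply is that pooling could hide a difference in how activity was called. Section 4.2.2 leaves the treating investigator unmasked, the call has a dosing consequence only in Arm B, and the BCVA and hemorrhage criteria require attribution to nAMD activity. This stands, and it is the reason to keep the by-arm rows beside the pooled one.

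A reader might go further and infer that the lack of a Q16W-versus-Q12W comparison leaves an objective unmet. The documents do not support that. The primary objective is "To evaluate the efficacy of RO6867461 on visual acuity when administered at 12- and 16-week intervals", which asks for each interval to be evaluated and not for the two to be compared. Section 1.3 sets the benchmark as outcomes comparable to those of frequent anti-VEGF monotherapy, which the planned differences from ranibizumab address. Section 6.5 also plans an exposure-BCVA model, reported outside the Clinical Study Report.

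**Conclusion.** The point holds as a low-cost improvement to one exploratory analysis. Pooling A and B at Week 24 narrows the 80% interval by 28-29%, from 18.5-22.8 to 13.2-16.3 points. This rests on assumed rates of 20-50%, about 30 assessed patients per arm, and activity having been called alike in both arms. No stated figure or primary analysis is wrong.

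Two stronger readings are tempting and fail:

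- **That the B-minus-A difference is the trial's most precise comparison of Q16W with Q12W.** The 4.47 letters apply only to the as-assigned comparison of Q12W with a Q16W strategy that allows a switch. For patients kept on Q16W, the rescaled half-width is 5.6-8.9 letters at 20-50% switched, wider than the planned contrasts with ranibizumab. Time since injection at Week 40 also differs, 4 against 12 weeks.
- **That restricting both arms to patients negative on the Week 24 criteria would isolate Q16W.** Status derived from BCVA and CST alone leaves out new macular hemorrhage and the attribution to nAMD. Arm B patients switched with Sponsor approval do not meet the criteria by definition, so they would stay in the negative group while on Q12W dosing. That analysis is not recommended.

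**What to change.** In Section 6.4.3, keep the proportion by arm and add the pooled A+B proportion with its 80% Wilson interval. Note beside it that planned treatment in the two arms is the same up to the assessment, and that pooling assumes activity was called alike. Pooled A+B change in BCVA and CST may be added in the same way for visits up to and including the pre-dose Week 24 assessment.

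Optionally, list the as-assigned B-minus-A difference in BCVA from the planned MMRM as descriptive. Label it as Q12W versus a Q16W strategy with a Week 24 switch, show it visit by visit without averaging, and give the total Arm B switch share (criteria-based plus Sponsor-approved) beside it. Do not describe it as the more precise estimate for Q16W itself. A few words naming the reference group for the odds ratios in Section 6.4.2 would remove an ambiguity.

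The cost is a sentence or two of SAP text and one table row, plus a small table for each option taken up. All data are already collected, and no visit, dose or primary analysis changes.

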6.5 PHARMACODYNAMIC ANALYSIS

An empirical drug-disease model of longitudinal BCVA previously developed on the ranibizumab database will be used to analyze the effect of RO6867461 on BCVA by using a meta-analysis approach.

A similar modeling approach will be used to analyze the relationship between RO6867461 exposure and BCVA. The influence of various baseline covariates on model parameters will be investigated. The PK/PD or dose/PD relationship will be

characterized. The results will be reported in a separate document from the Clinical Study Report.

6.6 SAFETY ANALYSES

The safety analyses will include all randomized patients who received at least one dose of the study treatment, whether prematurely withdrawn from the study or not, with patients grouped according to treatment received.

The original terms recorded on the eCRF by the investigators for adverse events will be standardized by the Sponsor. Adverse events will be summarized by mapped term and appropriate thesaurus level.

Separate summaries will be prepared for systemic and ocular adverse events, with events in the study eye and non-study eye summarized separately. Serious adverse events will be summarized similarly. Adverse events leading to discontinuation from the study will be listed and tabulated.

6.7 PHARMACOKINETIC ANALYSES

A non-linear mixed effects modeling approach (with NONMEM[®] software [[Beal and Sheiner 1998](#)]) will be used to analyze the concentration-time data of RO6867461. Population and individual primary PK parameters (i.e., clearances and volumes) will be estimated, and the influence of various covariates (e.g., gender, body weight) on these parameters will be investigated. The data collected in this study may be pooled with data collected in the previous studies, as appropriate, to build a PK model. Secondary PK parameters such as area under the concentration–time curve (AUC) and maximum concentration observed (C_{max}) will be derived from the individual post-hoc predictions. The result of this analysis will be reported in a separate document from the Clinical Study Report.

Additional PK analyses will be conducted as appropriate.

6.8 IMMUNOGENICITY ANALYSES

The immunogenicity analyses will include patients with at least one predose and one postdose ADA assessment, with patients grouped according to treatment received.

6.9 OPTIONAL INTERIM ANALYSES

Given the hypothesis-generating nature of this study, the Sponsor may choose to conduct up to two interim efficacy analyses. The decision to conduct an optional interim analysis and the timing of the analysis will be documented in the Sponsor's trial master file prior to the conduct of the interim analysis. The interim analysis will be performed by the Sponsor IMC (see Section 3.1.2) and appropriate senior management personnel who will be unmasked at the treatment group level. Access to treatment assignment information will follow the Sponsor's standard procedures.

7. DATA COLLECTION AND MANAGEMENT

7.1 DATA QUALITY ASSURANCE

The Sponsor will be responsible for data management of this study, including quality checking of the data. Data entered manually will be collected via EDC through use of eCRFs. Sites will be responsible for data entry into the EDC system. In the event of discrepant data, the Sponsor will request data clarification from the sites, which the sites will resolve electronically in the EDC system.

The Sponsor will produce an EDC Study Specification document that describes the quality checking to be performed on the data. Central laboratory data Central Reading Center data will be sent directly to the Sponsor, using the Sponsor's standard procedures to handle and process the electronic transfer of these data.

eCRFs and correction documentation will be maintained in the EDC system's audit trail. System backups for data stored by the Sponsor and records retention for the study data will be consistent with the Sponsor's standard procedures.

7.2 ELECTRONIC CASE REPORT FORMS

eCRFs are to be completed through use of a Sponsor-designated EDC system. Sites will receive training and have access to a manual for appropriate eCRF completion. eCRFs will be submitted electronically to the Sponsor and should be handled in accordance with instructions from the Sponsor.

All eCRFs should be completed by designated, trained site staff. eCRFs should be reviewed and electronically signed and dated by the investigator or a designee.

At the end of the study, the investigator will receive patient data for his or her site in a readable format on a compact disc that must be kept with the study records. Acknowledgement of receipt of the compact disc is required.

7.3 SOURCE DATA DOCUMENTATION

Study monitors will perform ongoing source data verification to confirm that critical protocol data (i.e., source data) entered into the eCRFs by authorized site personnel are accurate, complete, and verifiable from source documents.

Source documents (paper or electronic) are those in which patient data are recorded and documented for the first time. They include, but are not limited to, hospital records, clinical and office charts, laboratory notes, memoranda, patient-reported outcomes, evaluation checklists, pharmacy dispensing records, recorded data from automated instruments, copies of transcriptions that are certified after verification as being accurate and complete, microfiche, photographic negatives, microfilm or magnetic media, X-rays, patient files, and records kept at pharmacies, laboratories, and medico-technical departments involved in a clinical trial.

Before study initiation, the types of source documents that are to be generated will be clearly defined in the Trial Monitoring Plan. This includes any protocol data to be entered directly into the eCRFs (i.e., no prior written or electronic record of the data) and considered source data.

Source documents that are required to verify the validity and completeness of data entered into the eCRFs must not be obliterated or destroyed and must be retained per the policy for retention of records described in Section 7.5.

To facilitate source data verification, the investigators and institutions must provide the Sponsor direct access to applicable source documents and reports for trial-related monitoring, Sponsor audits, and IRB/EC review. The study site must also allow inspection by applicable health authorities.

